**REGULATORY FRAMEWORK:**

Please indicate all that apply:

	DOD (Department of Defense)
	DOE (Department of Energy)
	DOJ (Department of Justice)
	ED (Department of Education)
	EPA (Environmental Protection Agency)
	FDA (Food and Drug Administration)
	HHS (Department of Health and Human Services)
	Other:

Is this a clinical trial under ICH-GCP E6?  Yes  No

If yes, please confirm that the research team is familiar with and agrees to comply with the investigator requirements cited in ICH-GCP E6.  Yes  No

ICH-GCP E6 can be accessed by copying and pasting this URL into your browser: <http://www.fda.gov/downloads/Drugs/Guidances/ucm073122.pdf>

## **MEND (Mild Encephalopathy in the Newborn treated with Darbepoetin)**

11.18.2020

### **1. Objectives**

**Primary Hypothesis:** Darbe will improve neurodevelopmental outcomes in infants  $\geq 34$  week gestational age with mild encephalopathy who do not qualify for therapeutic hypothermia

#### **Specific Aims:**

- To assess the feasibility of administering one dose of Darbe in late pre-term ( $\geq 34$  week) and term infants with mild encephalopathy, who do not qualify for TH
- Establish population pharmacokinetics of Darbe in late pre-term ( $\geq 34$  week) and term infants with mild encephalopathy, who do not qualify TH
- To determine if Darbe improves neurodevelopmental outcomes in late pre-term ( $\geq 34$  week) and term infants who do not qualify for TH

### **2. Background**

Therapeutic hypothermia (TH) has become the standard of care for newborns diagnosed with moderate to severe neonatal encephalopathy (NE) at  $<6$  hours of age. However, in current practice TH is not indicated in newborns who are NOT classified as moderate to severe NE on a  $<6$  hours standardized neurological examination. Although perinatal acidemia is the initial screening component in the decision to treat the newborn with TH, the majority of newborns with perinatal acidemia do not receive TH because their neurologic examination is not abnormal enough to be classified as having moderate or severe NE. A retrospective review of infants found that as many as 20% of newborns who do not qualify for TH encephalopathy will have abnormal short-term outcomes such as seizures, death from progressive asphyxia insult, abnormal brain MRI consistent with NE, abnormal neurologic examination at discharge, gastrostomy tube feeding, or feeding difficulties in the NICU. Preliminary data from a multicenter, prospective study (PRIME study) show 36% of infants with mild HIE had either abnormal neurological exam, aEEG or MRI; only 2% (1 infant) had abnormalities in all 3 parameters. There are currently no therapies offered to infants with mild NE. Although, outcomes are thought to be better in infants with mild NE there is still a significant risk of neuronal injury in infants born with perinatal/fetal acidemia who are diagnosed with mild encephalopathy.

Neuroprotective strategies aimed at improving early childhood outcomes are needed. Erythropoiesis stimulating agents (ESA) have been shown to provide neuroprotection, improving short and long-term neurologic outcome in brain injury and NE in neonates. ESA may work through several important mechanisms including reduced inflammation, limited oxidative stress, decreased apoptosis and white matter injury, as well as via pro-angiogenic and neurogenic properties. Darbepoetin alfa (Darbe), a recombinant human erythropoietin (EPO)-derived molecule, has an extended circulating half-life and comparable biological activity to EPO. The proposed study is a Phase II trial of early Darbe administered to infants with mild NE. The long-term objective of the proposed research is to decrease the risk of long-term disabilities in infants with mild NE who do not qualify for hypothermia therapy.

### **Preclinical Trials**

In recent years, ESA have been studied extensively in preclinical trials of neuroprotection prompted by the finding that EPO receptor is expressed in the human brain (in cultured neurons, astrocytes, oligodendrocytes, microglia, and endothelial cells)(1-3). Importantly, both EPO and Darbe administered peripherally can cross the blood-brain barrier by way of extracellular pathways in amounts that can account for their neuroprotective actions.(4) Animal models have shown EPO to activate cellular mechanisms that promote cellular maturation, inhibition of apoptosis, neurovascular remodeling, revascularization and neurogenesis. (5-9) Exogenously administered EPO also enhances endothelial progenitor cell mobilization from the bone marrow, amplifies the production of neural progenitor cells, and stimulates oligodendrogenesis. (10-12)

With respect to the treatment of ischemic brain injury in experimental animal models of perinatal brain injury, systemic administration of EPO improves functional and histological recovery. EPO reduced infarct volume and improved functional and neurobehavioral performance when given immediately prior to or after neonatal brain injury using the Vannucci-Rice model for neonatal HI (13-16). Neurobehavioral testing revealed significant enhancement of muscle strength, limb placing reflexes, motor coordination and neurosensory skills. Recently, Traudt et al showed, in a non-human primate model of HIE, that EPO combined with hypothermia decreased death and moderate/severe cerebral palsy in comparison to placebo or hypothermia only. Additionally, neuroimaging studies were improved with combined EPO/hypothermia treatment. (17)

Similarly, Darbe administration following cortical impact injury in adult rats improved cerebrovascular function and reduced histological damage in a dose and time dependent manner(18). Weekly administration of Darbe conferred histological and behavioral neuroprotection after intracerebral hemorrhage in rats similar to that of EPO administration.(7, 19, 20)

Finally, following focal cerebral ischemia in rats (middle cerebral artery suture-occlusion), Darbe-treated rats showed decreased infarct volume and total infarct areas as well as improved neurologic scores relative to vehicle-treated animals. (20)

**In summary, there is convincing data in a variety of animal models that ESA can cross the blood-brain barrier and enhance neurological recovery following stroke, NE, and trauma. This is accomplished through several important mechanisms such as inhibition of apoptosis and enhanced neurogenesis.**

**Previous Human Experience**

**Adult Clinical Trials**

**ESA use in critically ill adult patients**

In recent years, EPO clinical trials have been designed to assess neuroprotection in a variety of conditions including stroke, subarachnoid hemorrhage, out-of-hospital cardiac arrest, and cardiac surgery(21-26). In these settings, the dose of EPO ranged from 30,000 U/dose X3 doses every 48 hours(26); 40,000 IU of IV EPO within 6hrs of symptoms, at 24h and at 48h(22); 40,000U IV q12h for the first 48h after ICU admission(23); or 375-1500 U/Kg x 3 daily doses(24).

The overall outcomes have been quite variable, ranging from favorable to no difference in the outcomes measured between treatment groups. Among favorable outcomes, Tseng observed that in those patients <60 years old and non-septic, the EPO group developed significantly less cerebral vasospasm, impairment in cerebral autoregulation and neurological deficits (as measured by the National Institutes of Health Stroke Scale)(26). Haljan et al. observed a trend in reduction of neurocognitive dysfunction in patients undergoing coronary artery bypass surgery who received increasing doses of EPO divided in 3 daily doses, starting the day before surgery(24). In a recent retrospective matched case control study of EPO and Darbe, Talving et al observed that ESA administration following severe traumatic brain injury in adult patients was associated with a significantly improved in-hospital survival rate without increase in morbidities in comparison to matched controls(25).

In some, but not all of these studies, EPO administration was associated with a higher rate of death, intracranial hemorrhage, thromboembolic events and brain edema (22) (23). These results are in contrast to a smaller trial in critically ill patients that were also treated with EPO but who **did not receive thrombolytic therapy**, as was the case in patients with the complications described above(21).

A 2016 analysis of ESAs in critically ill trauma patients found a significant improvement in mortality without an increase in the rate of proximal deep vein thrombosis(27).

**In conclusion, further studies of the potential therapeutic effects of ESA are warranted in select populations, such as newborns with hypoxic-ischemic injury at birth, with close monitoring of outcomes and adverse effects.**

**Studies of ESA in Premature Infants**

The administration of human recombinant EPO in preterm infants has been studied as an alternative to red blood cell transfusion in the treatment of anemia since the late 1980s. Between 1991 and 2009, 2,723 preterm infants were enrolled in 33 randomized controlled trials to evaluate the safety and efficacy of EPO as a treatment for anemia of prematurity. Treatment regimens varied widely, ranging from 70 to 5000 U/kg/week, with duration of therapy ranging from 2 weeks to several months. Halperin et al reported data from the first pilot study on the treatment of anemia of prematurity in 1990(28). Since

then, a multitude of studies have been performed examining a variety of EPO doses from low <500 U/kg/week to high >500 U/kg/week and treatment periods from early (started before 8 days of age) versus late (between 8 - 28 days after birth).(29-31). The NICHD NRN study of early erythropoietin therapy for anemia of prematurity examined the effects of EPO treatment (400 U/kg 3 X/ week) initiated by 4 days after birth and continued through 35 weeks postmenstrual age in preterm infants < 1250g birth weight. This study revealed no impact in transfusion requirement, but was important in that it demonstrated no increase in adverse events with similar rates of hospital morbidities, mortality, length of hospital stay, neutropenia, hypertension and seizures in the EPO treated and placebo/control infants. Follow-up at 18-22 months' corrected age revealed similar rates of neurodevelopmental impairment and need for rehospitalization between groups(32). Gumi-Pause et al studied higher doses (up to 5000 U/kg/week) of EPO and once again demonstrated no impact on episodes of infection, NEC, sepsis and neutropenia between low (1250 U/kg/wk) and "high-dose" (up to 5000U/kg/wk) EPO(33). In a small ancillary study to the NRN trial, 16 premature infants were treated with EPO or placebo for anemia of prematurity, and **Bierer et al reported an association between higher EPO levels (> 500 mU/mL) and higher Mental Developmental Index scores** on the Bayley Scales of Infant Development II at 18-22 months' corrected age(34). Similarly, **Brown et al** reported improved neurodevelopmental outcomes in a secondary analysis of 82 preterm infants born <1500g and < 30 weeks' gestational age treated with erythropoietin for anemia. **Increasing cumulative EPO exposure was associated with higher BSID II Mental Developmental Index scores (35).** Neubauer et al reported a similar beneficial effect on 10-13y outcome of 148 preterm infants treated with EPO under a variety of dosing regimens: the EPO group scored significantly better than untreated children in the overall developmental assessment (55% vs. 39% normally developed, p<0.05) as well as in the psychological examination (mean composite HAWIK-III IQ score, 90.8 vs. 81.3, p < 0.005)(36). **Over this wide range of dosing and duration of therapy, EPO and Darbe has been quite safe in neonatal populations. No study of EPO treated newborns has reported an increase in thrombotic complications similar to those observed in adults.**

Several recent single-center trials reported on the **safety and pharmacokinetics of "neuroprotective" doses of erythropoietin in premature infants** using doses that are approximately 10 fold higher than those used for anemia of prematurity. Juul and colleagues performed a prospective, open-label dose-escalation trial in which 30 infants were treated with high dose recombinant human erythropoietin (Epoetin Alfa Recombinant) and compared with 30 concurrent control infants(37). Infants received doses of 500U/kg/dose, 1000U/kg/dose or 2500U/kg/dose for three doses at 24 hour intervals starting on day 1, with ten infants in each group. The researchers found that both the 1000U/kg/dose and 2500U/kg/dose produced peak serum EPO concentrations that were analogous to neuroprotective concentrations seen in animal and adult studies. High dose EPO followed nonlinear pharmacokinetics as decreased clearance was observed with the highest dosing regimens. No increase in adverse events was reported for the EPO treated infants when compared with the control infants(37).

## **MEND (Mild Encephalopathy in the Newborn treated with Darbepoetin)**

11.18.2020

Fauchère and colleagues performed a randomized, double-masked trial in which preterm infants between 24 and 31 weeks GA were given recombinant human EPO (Epoietin Beta in doses of 3000U/kg birth weight) or placebo at 3, 12-18, and 36-42 hours after birth. A multicenter trial looked at preterm infants (26-32 weeks gestation) and found no improvement in neurodevelopmental outcome at 2 years corrected age, and no adverse effects using rhEPO 3000 U/kg.

Once again, **administration of high dose EPO resulted in no significant adverse events(38).**

Regarding the administration of Darbe in preterm infants, Warwood el al showed that a single dose of Darbe accelerated effective erythropoiesis in a pilot study of 12 preterm infants(39). The same group of investigators reported that IV administration to neonates resulted in a shorter half-life, a larger volume of distribution and more rapid clearance(40).

Ohls et al. performed a **randomized, placebo controlled study** to assess the safety and efficacy of **Darbe administered to preterm infants** (500-1250 grams birth weight). In this study they reported preterm infants who received ESAs (Darbe 10 $\mu$ g/kg or EPO 400 U/kg) had significantly better cognitive outcomes at 18-22 months and at preschool testing compared with placebo recipients, with no adverse events reported.(41)

Natalucci et al. recently published a study using prophylactic early high-dose recombinant human erythropoietin in preterm infants (26-31 weeks gestation). 228 participants were randomized to receive either erythropoietin 3000 IU/kg and 220 received the placebo. Erythropoietin was given IV at 3 hours, 12-18 hours, and at 36-42 hours after birth. They found that among infants who received prophylactic erythropoietin there was no significant difference in neurodevelopmental outcome between the groups. No adverse events were reported(42).

### **Trials of EPO in term infants with NE**

Recent studies have evaluated the use of EPO in **term infants with NE** not treated with hypothermia. The first was a randomized prospective study of 167 term infants with moderate/severe NE conducted by Zhu et al(43). Infants were randomly assigned to receive either EPO (N=83) or conventional treatment (N=84). EPO treated infants received either 300U/kg of rhEPO (N=52) or 500U/kg of rhEPO every other day for 2 weeks starting within 48 hours of birth. Study participants were followed to 18 months of age and underwent detailed neurodevelopmental assessment. Primary outcome was death or moderate/severe disability defined as CP, severe hearing loss, blindness, gross motor function classification levels 3 through 5, and a MDI <70 on the Bayley Scales of Infant Development II. Complete outcome data were available for 91.6% of participants. **EPO treated infants had significantly lower rates for death or moderate to severe disability** (24.6% [18/73] infants versus 43.8% [35/80]) in control infants; P=0.017). Subgroup analyses revealed benefit from EPO treatment only in babies with moderate NE. No differences in primary outcomes or side effect profiles were noted for the two studied EPO doses (43).

A study conducted by Elmahdy et al, was a pilot study that examined the safety and efficacy of much higher doses of EPO administration upon generation of nitric oxide (NO), a mediator of hypoxic injury. This was a case-control study with 3 groups of infants (15 infants per group). The first group was comprised of normal healthy term infants; the second was comprised of term infants with mild/moderate NE who were administered 2500U/kg of subcutaneous EPO daily for 5 days; and the third group was an NE control group that received no EPO. Baseline serum concentrations of NO were measured in the normal healthy neonates, and at baseline and 2 weeks for the two NE groups. In addition, the two NE groups underwent encephalography at baseline and 2-3 weeks and MRI at 3 weeks of age. Neurological assessment and neurodevelopmental screening (Denver Developmental Screening Test II) were performed at 6 months of age. Compared with the healthy term infants, the NE groups had higher serum NO levels. Though the two NE groups did not differ in severity of illness, NO levels, seizure burden or EEG background activity at baseline, the EPO treated group had statistically lower serum NO levels, fewer neurodevelopmental deficits and improved EEG background at follow-up. MRI findings did not differ between groups. No side effects related to EPO administration were identified despite close monitoring for allergic reactions, venous thrombosis, renal/hepatic effects, hypertension or electrolyte disturbances(44).

In 2012, an open label, dose-escalation, phase I study, enrolled 24 term infants undergoing TH for moderate/severe NE. Patients received 1 of 4 Epo doses intravenously: 250 (N=3), 500 (N=6), 1000 (N=7), or 2500 U/kg per dose (N=8). They gave up to 6 doses every 48 hours beginning at <24 hours of age. Epo did not follow linear pharmacokinetics, but excessive accumulation did not occur. At 500, 1000, and 2500 U/kg Epo,  $t_{1/2}$  was 7.2, 15.0, and 18.7, and the area under the curve was 50,306, 131,054, and 328,002 U\*h/L, respectively. They noted drug clearance at a given dose was slower than reported in uncooled preterm infants. No deaths or serious adverse events were seen. They found that Epo at 1000 U/kg given intravenously in conjunction with hypothermia is well tolerated and produces plasma concentrations that are neuroprotective in animals (45).

In 2016 a phase II double-blinded, placebo-controlled trial randomized newborns with moderate/severe NE to treatment with hypothermia alone or high-dose erythropoietin in addition to hypothermia. 50 infants were enrolled. They found that high-dose erythropoietin and hypothermia resulted in less MRI injury and improved neurodevelopmental outcomes at 12 months of age. There were no safety issues reported(45).

[figure not shown]
**The therapeutic potential of EPO and its chemical analog Darbe for NE brain injury in the newborn appears to be safe.**

## MEND (Mild Encephalopathy in the Newborn treated with Darbepoetin)

11.18.2020

### Low Dose vs. High Dose Darbepoetin

In 2015 a multi-center study was published to assess safety and pharmacokinetics of Darbe in infants undergoing TH for NE. It evaluated 30 term infants with moderate to severe NE who were undergoing hypothermia therapy and randomized to standard of care TH or TH and Darbe low dose (2  $\mu$ g/kg) or TH and Darbe high dose (10  $\mu$ g/kg) given intravenously within 12h of birth and at 7 days. Adverse events were documented for 1 month and pharmacokinetics were evaluated. Adverse events were similar to placebo and historical controls. Following the first dose (hypothermia conditions) at 2 and 10  $\mu$ g/kg,  $t_{1/2}$  was 24 and 32 hours, and the area under the curve was 26,555 and 180,886 h\*mU/ml\*, respectively. The clearance of the drug was not noted to be different between the doses. At 7 days (normothermia conditions),  $t_{1/2}$  was 26 and 35 hours, and the area under the curve was 10,790 and 56,233 h\*mU/ml\*, respectively(46).

This study showed that the 10  $\mu$ g/kg dose produced a median AUCinf of 180,886 h\*mU/ml after the first dose, which is comparable to previous report of neuroprotection in animal studies. (47)

**In summary, despite more than 20 years of use, few safety concerns have been identified with the use of ESAs in preterm and term infants. Furthermore, there is emerging evidence that early use of EPO or Darbe in extremely low birth weight infants can improve neurological outcomes. Additionally, recent research has given guidance as to the pharmacokinetics of Darbe in neonates with moderate/severe encephalopathy.**

### 3. Study Design

Eligible patients will be identified by the admitting neonatologist or by the research nurses based on admission diagnosis (perinatal depression, perinatal acidemia, HIE or NE, encephalopathy, clinical assessment for the need for therapeutic hypothermia).

**Inclusion Criteria:** Infants will be eligible for the MEND trial if they have a gestational age  $\geq$  34 weeks by best obstetric estimate, are <24 hours old and have evidence of mild encephalopathy and **DO NOT** have moderate-severe acute NE as defined by Shankaran et al based on a modified Sarnat examination performed at <6 hours of age (48).

Eligibility will include criteria presently used in the NICU to initiate therapeutic hypothermia and used in the NICHD NRN hypothermia trial:

- 1) History of an acute perinatal event (abruption, cord prolapsed, severe fetal heart rate abnormality, or meconium staining)
- 2) Infant is evaluated for hypothermia therapy and **DOES NOT** meet clinical criteria for TH.
- 3) Infant has an IV for clinical treatment

### Exclusion Criteria

- 1) Moderate/Severe encephalopathy on modified Sarnat examination at < 6 hours of age
- 2) Major congenital and/or chromosomal abnormalities
- 3) Prenatal diagnosis of brain abnormality or hydrocephalus
- 4) Severe growth restriction ( $\leq$  3% for gestational age)
- 5) Central venous hematocrit >65%, platelet count >600,000/dL, and/or neutropenia (ANC<500  $\mu$ L)
- 6) ECMO
- 7) Infant judged critically ill and unlikely to benefit from neonatal intensive care by the attending neonatologist

After eligibility is confirmed, with approval from the Attending Care Provider, the parent or legal guardian will be approached for consent (as noted below under consent process). All patients eligible for this study will be managed in the NICU.

**Drug administration:** Each center will obtain their own Darbe through their research pharmacies. Randomization will take place at each site using a provided block-design randomization table created by UNM research pharmacy. The site pharmacy will then dispense the study drug to the research nurse in a closed container. Darbe and vehicle are the same in appearance, and will be labeled “study drug”.

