#### **Standard of Care vs. Research-Related Procedures:**

Research-Related procedures:

1. Study drug can be given as soon as the infant is found to **NOT** qualify for TH but before 24 hours of age.
2. Extra 0.3 mL of blood drawn prior to drug administration (optional)
3. Neurological examination at discharge, transfer, or 96 hours of age (which ever occurs first)
4. Follow up phone calls at 4 months of age
5. Bayley Scales of Infant Development examination at 8-12 months corrected age.
- 6.

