### **Safety**

For the purpose of this study, an **adverse event** (AE) will be defined as any adverse change from the patient's baseline condition that occurred following the administration of the study drug through the end of the study period. Safety will be evaluated during the first 7 days of life or until hospital discharge (whichever comes first) by documenting potential adverse events such as (but not limited to) alterations in blood pressure, secondary infections, neutropenia, thrombotic/vascular events, hematologic events (platelets, Hct level, polycythemia), and hepatic/renal function that are outside of normal range for the study population.

We will assess for the rare complication (1 in 10,000 in adults with renal failure) of pure red blood cell aplasia. The vast majority of babies admitted to the NICU have a CBC with diff drawn on admission. If there is at least 0.5mL of blood remaining (scavenged blood) after analysis, we will collect that blood and use as our baseline sample. Similarly, most babies admitted to the NICU have electrolytes or bilirubin levels drawn at 24-72 hours of age, if there is at least 0.5mL of blood remaining (scavenged blood) after analysis, we will collect that blood and use as our second sample. If the baby remains in the NICU for 2 weeks (uncommon) and has a blood test done for clinical reasons, we will attempt to keep 0.5mL (scavenged blood) to assess for pure blood cell aplasia. Additionally, a letter (attached) will be given to the PCP stating that the patient is enrolled in a research study. If there are concerns for anemia and the PCP orders a CBC within the first year of life we will ask for 0.5mL of blood (scavenged blood). We will ask the lab to hold "scavenged" blood and store for up to 6 months beyond enrollment of the last patient.

We will also ask for the medical records from the child's primary care provider and their most recent hematocrit/hemoglobin.

**Long Term Safety** will involve phone calls at 4 months of age which will include developmental screening via Ages and Stages questionnaire, hospitalizations, seizures, need for assisted respiratory support, failure to thrive, medication use, use of early intervention services, hearing impairment, any concern with vision. In addition we will contact the child's primary care provider and ask for the child's medical records and most recent hematocrit/hemoglobin to assess for safety.

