**MEND (Mild Encephalopathy in the Newborn treated with Darbepoetin)**

11.18.2020

Evaluation	Screening	Pre-Entry (Prior to 24 hrs)	Entry (<24 hr of age)	discharge, transfer, or 96 hours of age (which ever occurs first)	3-10 days	Discharge	4 months corrected age	8-12 months corrected age
Screen admissions to NICU	X	X						
Documentation of Gestational Age		X						
Informed Consent		X						
Maternal Demographics and History			X			X		
Blood Pressure			X		X	X		X
Modified Sarnat Exam				X				
MRI as available from clinical care					X	X		
Hematology (CBC/transfusions/phlebotomy loss) as available from clinical care			X			X		X
Administration of study drug IV			X					
Liver/kidney Function Tests (as clinically available)					X			
Complete Physical Exam including weight, head circumference and length			X			X		
Telephone contact to review current status							X	
Ages and Stages phone questionnaire							X	
Phone/in person survey on hospitalizations, seizures, need for respiratory support, failure to thrive, medication use, use of early intervention, hearing impairment, concerns with vision							X	X
Neurodevelopmental assessment Bayley III & Standardized Neurologic exam								X
Weight, length, head circumference, blood Blood pressure, and heart rate								X

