### **6. Provisions to Monitor the Data to Ensure the Safety of Subjects**

The data and safety monitoring board (DSMB) is composed of members qualified by training and experience to monitor the progress of the investigation:

- 1) [name] Professor of Neurology, University of New Mexico. [name] will be the DSMB Chair for this project.
- 2) [name]. Professor of Pediatrics, University of New Mexico. [name] has led and conducted multiple multicenter clinical studies .
- 3) [name]. Division of Neuroscience, Department of Pediatrics, University of New Mexico
- 4) [name]. Professor of Pediatrics, Nationwide Children's Hospital, Columbus, Ohio.

Monitoring plan will include:

- 1) The DSMB will review the study data for non-compliance and participant safety (adverse events, unanticipated problems, etc.) after the first 20 patients have been enrolled and every 6 months until study completion

- 2) The DSMB will report their findings to the sponsor-investigator after each meeting
- 3) The sponsor-investigator will report DSMB findings to all participating clinical investigators after each meeting. Each participating investigator will submit the DSMB review to their IRB with corresponding documentation of the submission sent to [name]
- 4) All SAEs will be reported to [name] within 24 hours of the site learning of the event. Each site PI will be responsible for reporting the serious or unexpected adverse events to their local IRB in accordance with the local IRB policies. [name] will be responsible for notifying the DSMB chair within 24 hours of receiving the report and notifying the FDA in an IND safety report in accordance with FDA regulations. The DSMB will determine if the adverse event changes the risk to study subjects. If the information changes the known risk to subjects, the DSMB report of this event will be released to all participating investigators by [name].
- 5) Criteria for Withholding Study Drug: Neutropenia (ANC <500/ $\mu$ L), hematocrit of >65%, stroke, symptomatic clot, or hypertension (blood pressure 2 SD greater than the mean for age).

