## **7. Withdrawal of Subjects**

This is a single intervention study. If the infant is eligible and consented then the study drug will be given. After the delivery of the drug the intervention is complete. The family may choose to withdraw from the study at any time. Follow-up phone calls and neurodevelopmental testing will occur between 4-12 months of age.

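### Minor, wrong as written: exclusion criterion 5 prints the platelet limit per dL, which equals 6 per µL; the limit almost certainly meant is 600,000 per µL

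*Combined protocol and SAP*

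**What the plan says.** Section 3, Exclusion Criteria, item 5 excludes infants with "Central venous hematocrit >65%, platelet count >600,000/dL, and/or neutropenia". The neutrophil limit follows on the same line, expressed in µL.

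Platelets are mentioned in one other place. Section 3, Safety, includes "hematologic events (platelets, Hct level, polycythemia" among possible adverse events, with no numerical limit.

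Section 6, monitoring plan, item 5 begins "Criteria for Withholding Study Drug: Neutropenia", gives the ANC limit as <500/µL, and continues "hematocrit of >65%, stroke, symptomatic clot, or hypertension (blood pressure 2 SD greater than the mean for age". Platelets are not on that list.

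Three statements bear on the optional note about dosing:
- Section 7, Withdrawal of Subjects: "If the infant is eligible and consented then the study drug will be given".
- Section 3, research-related procedures: "Study drug can be given as soon as the infant is found to" not qualify for hypothermia, and before 24 hours of age.
- Section 3, after the exclusion list: "After eligibility is confirmed, with approval from the Attending Care Provider, the parent or legal guardian will be approached for consent".

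The schedule of evaluations puts blood pressure, study drug administration and "Hematology (CBC/transfusions/phlebotomy loss) as available from clinical care" in the same Entry column.

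**The concern.** A platelet exclusion at 600,000 is plainly meant to keep out infants with a very high count. With the printed denominator it does the reverse: the limit falls so low that any ordinary count exceeds it. This is a threshold that staff at several centres apply before consent, so it should be right as printed.

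The Section 6 withholding list raises a lesser matter. Two of its five criteria (ANC and hematocrit) are also exclusions. The other three (stroke, symptomatic clot, hypertension) are not, so an infant with one of them could be eligible, consented and randomised before the withholding rule is applied. Section 7 does not refer to that rule, and no text says whether the check comes before or after randomisation. At stake is the clarity of the dosing instruction for a handful of infants at most.

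**Working it through.** **Platelet unit**

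Input: the limit in exclusion 5, 600,000 per dL. The document shows no calculation behind it, so there is no derivation to reproduce, only a unit to convert.

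1. 1 dL = 100 mL = 100 × 1,000 µL = 100,000 µL.
2. Printed limit: 600,000 per dL ÷ 100,000 µL per dL = 6 per µL.
3. Limit with the unit corrected: 600,000 per µL × 100,000 = 6.0 × 10^10 per dL.
4. Ratio: 600,000 ÷ 6 = 100,000.
5. Plausibility: take an ordinary count of 150,000 per µL (an assumption; the document gives none). That is 1.5 × 10^10 per dL, or 1.5 × 10^10 ÷ 600,000 = 25,000 times the printed limit. Read literally, the criterion excludes every infant, so per dL cannot be what was meant.

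The only other mention of platelets carries no limit, so nothing in the document corrects the unit.

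**Withholding list against exclusion list**

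| Section 6 criterion | Also a Section 3 exclusion? |
|---|---|
| ANC <500/µL | Yes, item 5 |
| Hematocrit >65% | Yes, item 5 |
| Stroke | No |
| Symptomatic clot | No |
| Hypertension, 2 SD above the mean for age | No |

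The document gives no frequency for the last three, and stroke and clot cannot be quantified from it. For hypertension alone, assume normally distributed blood pressure, infants like the reference population and one reading each.

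- Upper tail beyond 2 SD = 0.02275.
- Infants affected: 80 × 0.02275 = 1.82 in the trial; 40 × 0.02275 = 0.91 on Darbe.
- At an assumed share of 1%: 0.8 of 80. At 5%: 4 of 80.
- If these infants were withheld after randomisation and so gained no benefit, the intention-to-treat difference would shrink by the withheld share, about 2.3% of its size (1% to 5%).
- If they were screened out first, randomising 80 would take 80 ÷ 0.97725 = 81.9 consented infants, about 2 more. The range is 80 ÷ 0.99 = 80.8 to 80 ÷ 0.95 = 84.2, or about 1 to 5 more.

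**The case against.** On the unit, the strongest reply is that this is a proofreading slip. Nobody could apply the limit literally and still enrol, so no infant, estimate or error rate is affected. The factor of 100,000 measures the slip, not its consequence. All of that stands and is why the point is minor. A reader might infer that eligibility was unworkable or that the wrong infants were excluded; the document does not support that. A fault in reading the PDF also cannot be fully ruled out, although the µL symbol later on the same line came through. The slash missing from the neutrophil limit on that line may well be such a fault, and Section 6 has the correct form, so nothing is claimed from it.

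On dosing, a reader might infer that Section 7 requires treatment of an infant with stroke, clot or hypertension, in conflict with Section 6. The text does not bear that out. The Section 7 sentence sits under withdrawal and explains that there is one dose and nothing to stop afterwards. With one dose, the Section 6 rule can act only before it, and a specific safety stop naturally overrides a general statement. The procedures list is merely permissive. Nor need withholding criteria match exclusions, since events can arise between eligibility and dosing.

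A reader might also point to Section 8, which lists clots, raised blood pressure and stroke. It attributes them to adult use and adds that there is no information to date of an increase in infants. They cannot be presented as established risks in this population.

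**Conclusion.** The platelet limit in exclusion 5 is wrong as written: it equals 6 per µL, and the evident intent is 600,000 per µL. This rests on the unit conversion and on the supplied text matching the source PDF. Severity is minor and the practical effect negligible, because sites would almost certainly read the limit as intended.

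The relation between Sections 6 and 7 is not an error. What remains is a missing cross-reference and an unstated time for the check, both of which sites would be expected to handle sensibly. The figure of about 2 infants in 80, with dilution of about 2.3%, covers hypertension only and rests on the normality, reference-population and single-reading assumptions; the 1% to 5% range is also assumed. It shows no material effect on the result. Section 5 already keeps every randomised infant in the analysis, so the analysis text needs no change.

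**What to change.** Check the printed unit against the source PDF. If it stands, amend the limits in exclusion 5 to read: *platelet count >600,000/µL, and/or neutropenia (ANC <500/µL)*. This costs one line in the next amendment.

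Optional clarification: add to the Section 7 dosing sentence *unless a Section 6 withholding criterion is present*, and state when the check is made. Before randomisation is preferable, using the blood pressure and clinically available hematology already collected at entry. No new test is needed; only the order relative to randomisation has to be stated. The drawback is that an early check acts as an added exclusion and may screen out a few infants, for example on one high blood pressure reading, so the team may wish to say how such a reading is confirmed.
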